### Describing the population

The index date "T0" is defined as the day upon which the beneficiary received a first dose of mepolizumab. Population characteristics will be tabulated at this time point and will include age, gender, area and region of residency, universal medical coverage status, and complementary health insurance status.

The population will be further described by providing the duration of treatment with mepolizumab (ie medication persistence (Cramer et al. 2008), defined as date of last administration – T0 in days) as well as the proportion of days of follow-up covered (PDC) by mepolizumab. The current authorized dosage for mepolizumab is a single 100 mg subcutaneous injection every 4 weeks (with an authorized leeway of +- 7 days), and the PDC will be determined accordingly.

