### 8.3.1.1. Mepolizumab exposure

Mepolizumab exposure will be characterized by cumulative numbers of injections and dosage.

Medication persistence is defined as the duration from T0 to the discontinuation of therapy (Cramer et al. 2008)(or the end of follow-up for the present study).

The proportion of days of follow-up covered (PDC) by mepolizumab (or the anologous medication possession ratio for dispensations) will also be calculated as the best available proxy for adherence and an important covariate for analyses or defining subgroups.

If mepolizumab is administered during a hospital stay, the dispensation might not be captured. This possibility will be explored by juxtaposing uncovered (non-PDC) time with hospital stays and investigating two extreme hypotheses: either all such stays contained the missing administration, versus no such stays contained the missing administration. This will provide minimum and maximum possible ranges for mepolizumab exposure.

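### The hospital-dose rule in section 8.3.1.1 does not give the maximum exposure it claims: under the protocol's own 28 ± 7 day interval, its upper limit can fall below the true exposure

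*Protocol*

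**What the plan says.** Protocol section 2 (Describing the population) gives the dosage as a "single 100 mg subcutaneous injection every 4 weeks (with an authorized leeway of +- 7 days), and the PDC will be determined accordingly". It does not say whether one dose counts as 28 or 35 covered days.

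Section 8.3.1.1 describes exposure by number of injections, dosage, persistence and PDC, and names PDC as a covariate or a basis for subgroups. It then notes: "If mepolizumab is administered during a hospital stay, the dispensation might not be captured". The remedy is to explore this by "juxtaposing uncovered (non-PDC) time with hospital stays and investigating two extreme hypotheses: either all such stays contained the missing administration". The opposite extreme is that none of those stays held it. The section closes with a claim about the result: "This will provide minimum and maximum possible ranges for mepolizumab exposure".

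**The concern.** The search for a missed dose starts from uncovered time, but a dose need not be given in uncovered time. The authorized interval lets it come up to 7 days before the previous dose's 28 days run out. The stay that held it may then be over before the gap opens, so the rule never considers it, and both extremes omit a dose the patient received.

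The rule can also err the other way. Taken literally, it credits every stay in uncovered time, whether or not a dose could have been given then without breaking the interval.

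What is at stake is the label. A reader will take a range called minimum and maximum possible as certain to contain the truth. The error also arises through hospital stays, which are themselves an outcome and a component of cost, so an analysis adjusted for or grouped by PDC would carry an error linked to its outcome.

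**Working it through.** The protocol states no figure for this rule, so there is nothing to reproduce. The check applies the rule to records that obey the protocol's interval.

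**Inputs from the protocol.** Interval 28 ± 7 days, that is 21 to 35 days (section 2); follow-up of 12 months, taken as days 0 to 364 (section 3.1); the crediting rule (section 8.3.1.1). **Assumed.** A dose on day d covers days d to d + C − 1, with C = 28 or 35 and no carry-over of overlapping days.

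**1. Maximum too low.** Doses fall on days 0, 28, …, 364, which makes 14, except that the day-140 dose is given on day 138, in a stay on days 137–139, and is not captured. The intervals around it are 138 − 112 = 26 and 168 − 138 = 30 days, both within the leeway.

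- C = 28, captured doses only: the day-112 dose covers to day 139, so days 140–167 (28 days) are uncovered. The stay ends on day 139 and is not in uncovered time. Minimum = maximum = 13 injections, PDC = 337/365 = 92.3%.
- C = 28, truth: the day-138 dose covers days 138–165, leaving days 166–167. That is 14 injections, PDC = 363/365 = 99.5%.
- C = 35, same record: the day-112 dose covers to day 146, so days 147–167 (21 days) are uncovered. The stay is again missed. The maximum is 13 injections and 344/365 = 94.2%, against a true 14 and 100%.

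**2. A stay that does not adjoin the gap.** Captured doses on days 0 and 49; hospital dose on day 21 in a stay on days 21–24; intervals 21 and 28 days. With C = 28 the gap is days 28–48. The stay ended four days before it opened.

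**3. Share of the permitted window that escapes.** For a one-day stay, any of the 15 days 21–35 is allowed. With C = 28, days 21–27 escape: 7/15 = 47%. With C = 35, days 21–34 escape: 14/15 = 93%. For a stay of L days with the dose on a random day of it, the share is (1/15L) × Σ over D = 21…35 of the number of k in 0…L − 1 with D + k < C. Timing uniform over the window is an assumption.

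| Stay length (days) | 1 | 3 | 5 | 7 | 10 |
|---|---|---|---|---|---|
| C = 28 | 47% | 40% | 33% | 27% | 19% |
| C = 35 | 93% | 87% | 80% | 73% | 63% |

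If every dose falls exactly on day 28, the share is 0% for C = 28 and 70–100% for C = 35.

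**4. Credits that do not fit the interval (C = 28, literal reading).**

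- Captured doses on days 0 and 33, on schedule: days 28–32 count as uncovered. A stay on days 29–31 is credited with a dose 2 to 4 days before a captured one, although none is missing.
- Captured doses on days 0 and 56, stays on days 30–32 and 40–42: both are credited, but the widest possible spacing is 42 − 30 = 12 days, below 21.

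**5. Frequency, on assumed inputs only.** A simulation used intervals uniform on 21–35 days, 0.5 to 4 random stays a year, mean length 3 to 8 days, and every hospital dose uncaptured. Among patients with such a dose, the maximum count was below the truth in 19–33% (C = 28) and 55–78% (C = 35). At one stay a year of mean 5 days, about 16% of patients had such a dose, so the share of the whole cohort was 0.160 × 0.252 ≈ 4% and 0.159 × 0.662 ≈ 11%.

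**The case against.** **The wording allows kinder readings.** Juxtaposing could include stays that merely adjoin the gap, which would catch the first record with 28-day cover. It would not catch the day 21–24 stay, and one-day stays on days 21–26 (6/15 = 40%) would still escape. The singular reference to the missing administration could mean one dose per gap, and only where one is missing. That arguably removes the double credit and the false credit in an on-schedule interval, so this second direction of error holds only on the literal reading.

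**Only one cover length can apply.** The credit in an on-schedule interval needs 28-day cover; the largest undercounts need 35-day cover, so they should not be added together. Neither choice makes the upper limit a bound.

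**A reader might infer that the maximum is often too low.** The documents do not support a frequency. They give no dose-timing distribution, stay rate or non-capture rate, and section 2 says inpatient data include consumption of costly drugs, so non-capture may be rare.

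**A reader might also infer that some maxima are impossible, or that hospital-treated patients always look less adherent.** An interval under 21 days is outside the authorized schedule, not impossible in real-life records. Many hospital doses would be found, particularly with 28-day cover.

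**Such details belong in an analysis plan.** Overlap, adjacency and counting per gap do. But the protocol itself fixes the rule and claims a property for its result, and that claim is what fails.

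**Conclusion.** The point holds as a minor one. The rule's upper limit is not a maximum: one record consistent with the protocol's own interval is enough to show it, and the example in step 1 falls short by one injection and 26 covered days (7.1 points of PDC) with 28-day cover. This needs only the 21–35 day window and the possibility of non-capture that the protocol itself raises. The minimum, which credits nothing, is not in question.

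The percentages in steps 3 and 5 illustrate the size under stated assumptions and are not estimates for this cohort. The undercount arises only in patients with an uncaptured hospital dose. The primary endpoint is a paired comparison of total cost and does not use PDC; the subgroup list in section 8.3.4 does not include PDC, and section 1.3 already concedes that actual exposure cannot be measured. The consequence is confined to the exposure description and to any analysis using PDC as a covariate or subgroup.

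**What to change.** Amend section 8.3.1.1 so that the interval between captured doses, not uncovered days, selects the stays:

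- A stay is a candidate if any of its days is at least 21 days after the previous captured or credited dose and at least 21 days before the next captured dose, whether or not those days count as covered.
- After the last captured dose, use any stay day from 21 days onward to the end of follow-up, with no minimum gap. A requirement of more than 35 days would miss, for example, a hospital dose on day 360 after a last captured dose on day 335.
- For the maximum, credit no more doses than fit with 21-day spacing. Find the largest injection count and the largest PDC separately over the allowed placements. Crediting in date order is not enough: with captured doses on days 0 and 56, one-day stays on days 21 and 28, and 28-day cover, crediting day 21 leaves days 49–55 uncovered, while crediting day 28 leaves none.
- Describe the range as the minimum and maximum consistent with the authorized interval.

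On the first record the window is days 133–147, so the stay qualifies. The maximum becomes 14 injections and, with 28-day cover and the dose placed on day 139, 364/365 = 99.7%, which now contains the truth. In the 33-day interval no day qualifies. In the two-stay gap (days 0 to 56) the window is days 21–35, so only the first stay does.

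The 28 ± 7 day figures serve only to classify records. The cost is a few sentences and slightly more programming, with no new data. The downside is a wider range for patients with stays just before a gap.

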#### Costs

Cumulative per-beneficiary costs (including all health care resource uses and government benefits) will be described and contrasted between the baseline and exposure periods. This will be performed at several levels: (i) all costs regardless of source or potential link with diagnoses, (ii) costs due to mepolizumab, (iii) costs that can be associated with asthma-specific care, (iv) costs that can be associated with the monitoring and care for certain key comorbidities (diabetes, bone density/osteoporosis).

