# 3.2. Participant and Study Completion

This study is primarily descriptive and the identification of beneficiaries receiving mepolizumab will be exhaustive. In this context, traditional sample size calculations are inappropriate/unnecessary. A first estimate indicates an expected sample size of 2813 patients (see section 10.1)

As concerns exclusion from the analysis due to missing data, we expect this to be minimal as the databases are exhaustive and obligatory concerning drug dispensations.

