#### 8. Statistical Considerations

# **8.1.** Sample Size Determination

This study is primarily descriptive and the identification of beneficiaries receiving mepolizumab in the SNDS will be exhaustive. In this context, traditional sample size calculations are not appropriate/unnecessary.

A first, preliminary analysis of the EGB, a 1/97th random permanent sample of the SNIIRAM French national database (Bezin et al. 2017), currently yields 29 beneficiaries having received mepolizumab during the 11 month period starting in February 2018 and ending in December 2018. We therefore aim to analyze data for approximately  $29 \times 97 = 2813$  beneficiaries receiving mepolizumab with 1 year of follow-up time.

Considering a type I error rate of 5% ( $\alpha$ =0.05), a sample size of 2813 yields *a posteriori* power estimates of 90% or better for cohen's effect sizes superior to 0.063 (Figure 10-1). The latter indicates ample power to detect very small effects (an effect size of 0.2 is considered as "small").

[figure not shown]

Figure 8-1 Effect size versus power for paired t-tests or for paired Wilcoxon tests (non-parametric option) when the type 1 error rate is set at alpha=0.05 and a sample size of 3000 is expected.

NB: This preliminary sample size analysis also served as a testing ground for the primary patient-selection algorithm (based on medication codes UCD 9413850 // code CIP\_C13 3400930038352), which is now finalized.

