# 8.3. Statistical Analyses

### **8.3.1.** General considerations

Children and adult patient data will be analyzed (no age limits will be imposed).

Descriptive statistics for quantitative variables will include sample size and number of missing values, range, median (interquartile range), and mean ± standard deviation. Summary statistics for qualitative variables will include sample size and number of missing values, the frequency and percentage (over non-missing values unless otherwise specified) for each category. All applicable statistical tests will be performed using a bilateral 5% significance level. All confidence intervals (CI) presented will be 95% and two-sided.

The lost to follow-up patients (e.g. exit from one of the insurance schemes available in the SNDS, expatriation with exit from French insurance schemes) will not be included in the study. No replacement of missing values will be performed. For a given patient with a complete follow-up period, all reimbursed healthcare consumptions are reported in the database.

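### The bounds for uncaptured in-hospital mepolizumab stop at exposure, so the mepolizumab cost line can be understated after T0 with no range shown

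*Protocol*

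**What the plan says.** Section 8.3.1.1 recognises that a dose given in hospital may leave no dispensation record. It plans to match uncovered time against hospital stays under two extremes: every such stay contained the missing dose, or none did. The stated product is limited to exposure: "This will provide minimum and maximum possible ranges for mepolizumab exposure".

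The Costs paragraph of section 2 lists four cost levels. The first is all costs, and the second is "ii) costs due to mepolizumab". The primary endpoint is total health care cost in the year before and the year after initiation.

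Section 8.3.1.2 values care at amounts reimbursed (Health Insurance perspective) or at amounts presented for reimbursement, with hospital stays at ENCC costs (Collective perspective). Neither that section nor 8.3.1.3, 8.3.2 or 8.3.3 mentions the two scenarios.

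Two other passages describe the data as complete. Section 3.2 says the "databases are exhaustive and obligatory concerning drug dispensations". Section 8.3.1 says that, for a patient with complete follow-up, "all reimbursed healthcare consumptions are reported in the database", and that missing values will not be replaced.

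**The concern.** The protocol names a capture gap for the study drug, sets out a way to bound it, and applies the bound to a descriptive variable but not to the cost of the same drug. One administration may then count as given in the maximum exposure scenario and contribute nothing to mepolizumab cost.

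For uncovered time after T0, which is all that section 8.3.1.1 examines, the error in that cost line has one direction. T0 is the first recorded dose, so the recorded baseline mepolizumab cost is zero and a missed dose after T0 lowers only the exposure-year figure. The confidence intervals in section 8.3.1.3 would not show this, because it is a capture error and not sampling variation. A reader would see a range for exposure beside a single figure for its cost, in a study whose hypothesis is that overall costs fall.

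**Working it through.** **The plan's own figure.** Section 8.1 starts from 29 users in a 1/97 sample: 29 × 97 = 2813, which reproduces. It states "power estimates of 90% or better for cohen's effect sizes superior to 0.063". With a two-sided 5% test ("All applicable statistical tests will be performed using a bilateral 5% significance level"), power ≈ Φ(d√n − 1.96) = Φ(0.063 × 53.04 − 1.96) = Φ(1.38) = 91.6%. For the Wilcoxon test, with effective n = 2813 × 3/π = 2686, power is 90.4%. The statement is correct and the present point does not depend on it. N is used only in the last step below.

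**Share of cost per dose.** Input: one injection every 4 weeks (section 2, Describing the population).
- Injections on days 0, 28, …, 364 number 14 including T0, or 13 after T0 (365/28 = 13.04).
- One uncaptured dose is 1/14 = 7.1% to 1/13 = 7.7% of that patient's full-year mepolizumab cost.

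**Average over the cohort.** The protocol gives no frequency of uncaptured in-hospital doses. ASSUMPTION: 5% to 30% of patients have 1 to 3 such doses each.
- Low end: 0.05 × 1 = 0.05 doses per patient; 0.05/14 = 0.4%.
- High end: 0.30 × 3 = 0.90 doses per patient; 0.90/13 = 6.9%.

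**Does total cost move as well?** The stay is itself costed, so there are two cases.
- The dose price is already inside the stay cost. The total is then complete, and only the split between hospital and mepolizumab cost is wrong.
- The dose price is not inside it. The total then falls short by the same amount of money as the mepolizumab line.

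The protocol does not say which case applies, and the answer may differ between the two perspectives.

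**Scale in the second case only.** The 95% half-width for a paired mean is 1.96/√2813 = 0.037 SD. The SD of the paired cost difference is not given. ASSUMPTION: it is worth 5, 14 or 28 doses. The mean number of uncaptured doses that equals the half-width is then:
- 1.96 × 5/53.04 = 0.18
- 1.96 × 14/53.04 = 0.52
- 1.96 × 28/53.04 = 1.03

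The assumed 0.05 to 0.90 doses per patient runs from well below the half-width to above it, depending on the SD.

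**The case against.** A reader might infer that the primary total cost is understated. The documents do not support that. The stay is valued at the amount reimbursed or at ENCC cost and may already include the drug. On the Health Insurance perspective the endpoint is what was reimbursed, and section 8.3.1 says all of that is recorded. Adding a dose price to such a stay would count it twice. Holding back the price only where the stay lists mepolizumab among the costly drugs (section 2, Information available in the SNDS) does not help, because a listed dose is a captured dose. This objection stands and limits the point to mepolizumab cost.

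A reader might also infer that the gap can fall only in the exposure year and can never offset between periods. That is too strong. If the first dose was given in hospital and not captured, the recorded T0 is late and the missed dose falls in the recorded baseline year. The section 8.3.1.1 check uses uncovered time after T0 and cannot see this.

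Three further arguments carry some weight.
- The maximum scenario is a deliberate extreme. It may include stays after treatment has stopped, so it is a bound and not an estimate of money spent.
- The completeness statements can be read as concerning exclusions and reimbursed care, not the itemising of every in-stay dose. They therefore need qualifying, and are not plainly false.
- A cost sensitivity analysis could sit in a statistical analysis plan that is not at hand. However, the protocol itself raises the gap and confines the remedy to exposure, so the limit is stated in this document.

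**Conclusion.** The point holds for the mepolizumab cost line. The plan recognises a gap in capture, bounds it for exposure, and leaves the cost of the same drug unbounded. After T0 the possible error is one-directional, at 7.1% to 7.7% of a patient's full-year mepolizumab cost per uncaptured dose. The cohort average is 0.4% to 6.9%, but only under the assumed frequencies; the true frequency is unknown.

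For the primary total cost the question is open. The protocol does not say whether in-hospital doses are inside the stay cost, so understatement there is possible but not established. This is a cheap improvement and a clarification, not a demonstrated bias in the primary result.

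**What to change.** In section 8.3.1.2:
- Report mepolizumab cost under both scenarios of section 8.3.1.1, valuing each imputed administration at the patient's own captured price per delivery.
- State, separately for the Health Insurance and Collective perspectives, whether doses given in hospital are inside the recorded stay cost.
- Where they are not, also report the primary total-cost difference under both scenarios as a sensitivity analysis.
- Where they are, treat the imputed amount as a move from hospital cost to mepolizumab cost, with nothing added to the total.

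Elsewhere, qualify the completeness statements in sections 3.2 and 8.3.1 so that they agree with section 8.3.1.1. Note as a limitation that an uncaptured first dose in hospital would shift T0 and lies outside these bounds.

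The cost is one extra sensitivity analysis built on scenarios already planned. Mepolizumab cost would appear as a range that may be slightly less favourable.

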#### 8.3.1.2. Costs

Economic assessments will be performed based on the Health Insurance (costs endorsed by national health insurance) and Collective (complementary insurance and remaining out of pocket charges) perspectives. For the Health Insurance perspective, the consumption of care will be valued according to the amounts reimbursed, and, for the Collective perspective, according to the amounts presented for reimbursement. In the latter, the hospitalizations will be valued according to the costs resulting from the ENCC (National Study of Costs with Common Methodology). All costs will be discounted to the year corresponding to the data access date.

#### 8.3.1.3. Statistics associated with specific endpoints

Endpoint	Statistical Analysis Methods
Primary (total costs)	Differences between the two study periods will be presented with their 95% confidence intervals, as well as significance testing for paired data (see the next section (10.3.2)). Changes in total costs with time will also be visually presented using mean cumulative function step curves (see section 10.3.3).
Secondary (health resource use and sub-costs)	The same strategies as for the primary endpoint will be employed (see the next section (10.3.2)).
Sub group analyses	The same strategies as for the primary endpoint will be employed (see the next section (10.3.2)).

#### 8.3.2. Comparing health resource usage and costs before and after T0

Descriptive statistics for the different types of health resource usage and their associated costs will be calculated for both the baseline and exposure periods. Differences between the two study periods will be presented with their 95% confidence intervals. Statistical techniques for paired data (paired t-tests, paired Wilcoxon tests) will be used to compare variables between the two periods. Potential covariates/subgroups-of-interest will be tested via interaction terms (covariate x period interactions) in mixed models with patients as fixed effects or via regression models explaining the change in resource use ( $\Delta$ baseline period-exposure period). Due to the descriptive and exploratory nature of this study, results will be presented with and without the application of a False Discovery Rate (FDR) correction for multiple testing.

